11.3 Statistical Methods

We will first conduct exploratory analyses to assess the completeness and distributional properties of all variables, including an exploration of location (e.g., means for continuous variables and frequencies and percentages for categorical variables), spread (e.g., ranges, standard deviations), and shape (e.g., normal, skew). Missing baseline sociodemographic data will be imputed using single or multiple imputation technique if the proportion missing is $<10\%$ or $\geq 10\%$, respectively. After enrollment, we will compare dropout rates and characteristics of subjects who drop out or are lost to follow-up to assess potential for bias. In cases of missing viral load data, we will treat the result as detectable, in accordance with our primary ITT analytic approach, similar to other studies. Our primary analyses will be by ITT, but we will also conduct per protocol analyses via logistic regression models to estimate treatment effects.

Sociodemographic, behavioral, and clinical attributes at baseline will be compared between Cohort 1 and Cohort 2 and Cohort 1 and Cohort 3 using Chi Square and Fisher Exact test for categorical variables and T-test and Wilcoxon and Kruskal-

Protocol Title: **CAB-RPV LA Implementation Strategies for High-Risk Populations**

Wallis tests for continuous variables. Differences in engagement in care will be examined in two separate models to compare Cohort 1 vs Cohort 2 and Cohort 1 vs. Cohort 3. We will construct a multivariable logistic regression model with a logit link and the events/trials syntax to model the outcome. The inclusion of key baseline variables for adjustment will be based on a p value of ≤ 0.2 in the bivariate analysis or clinical significance. The following regression equation will be used:

$$\text{Engagement in care} = \alpha + \beta_1 * \text{ixgroup}_1 + \beta_2 * \text{factor}_1 + \dots + \beta_n * \text{factor}_n + \varepsilon,$$

where ixgroup_1 is a dummy variable for cohort assignment, α is the intercept, $\beta_1, \beta_2, \dots, \beta_n$ is a vector of possible coefficients, and ε is an error term. Similarly to examine adherence we will use a multivariable logistic regression with a dichotomous outcome for undetectable viral load status at 6 months. Potential confounders will be examined using methods described above and entered into the final model based on a p value of ≤ 0.2 or clinical significance. We will conduct stratified analyses based on gender and other risk attributes (e.g. homelessness, substance use, etc.), though this will be exploratory, given the cohort study's pilot nature and our sample size.

12. Budget Justification

Our total enrollment into Objective 2 remains 60 participants. Therefore, the resources necessary to accomplish the scope remain unchanged, and we are not requesting a budget increase.

13. Ethics/Protection of Human Subjects

This study will be conducted according to applicable US federal regulations and institutional policies (which are based in federal regulations, guidance, and ICH Good Clinical Practice guidelines). This protocol and any amendments will be submitted to the Boston Medical Center/Boston University Medical Campus IRB, for formal approval of the study conduct. The decision of the IRB concerning the conduct of the study will be made in writing to the investigator.

All subjects for this study will be provided a consent form describing this study and providing sufficient information for subjects to make an informed decision about their participation in this study. The consent form will be submitted with the protocol for review and approval by the IRB. The consent of a subject, using the IRB-approved consent form, must be obtained before that subject is submitted to any study procedure. Consent will be documented as required by the IRB.

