6.0 Study Intervention

The study intervention for Cohort 1 is delivery of HIV medication at Project Trust, rather than in the BMC HIV Clinic. Project Trust (PT) is a street-based drop-in clinic that is focused on STD testing, treatment, harm reduction, and social services engagement. PT engages in outreach work, provides individuals with substance use disorder safe injection kits, and is a well-established community site for the target population frequenting the area, which is home to a high number of individuals who are homeless, diagnosed with substance use disorder, and are living with HIV. Study staff who will be administering the injection are all trained clinicians (either nurse practitioners or physicians) and are BMC staff. Individuals administering the injection will all be listed on the BUMC Internal Review Board study protocol.

There is not a clinical intervention or any intervention beyond data collection for Cohorts 2 or Cohort 3. Cohort 2 will be receiving their CAB-RPV LA within the BMC HIV clinic as their standard care. Cohort 3 will be receiving standard of care (not CAB-RPV LA) and will be patients of the BMC HIV clinic. Individuals enrolled in all three cohorts will be asked to complete a survey at study enrollment (baseline), between 2-4 months after their enrollment (midpoint) and a final follow up between 6 - 8 months post baseline. Clinical data will be obtained from the BMC EHR via the clinical data warehouse at these time periods and no other data will be collected directly from study participants for Objective 2.

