7.2 Cohorts 2 & 3 Recruitment, Screening & Enrollment

Cohort 2 Recruitment and Enrollment: Participants for Cohort 2 will be individuals who are receiving HIV in care at BMC's Center for Infectious Diseases (CID) and are receiving CAB-RPV LA. CID pharmacists and providers will approach all individuals who are actively receiving CAB-RPV LA and assess whether they are interested in participating and ask them to complete the Screening Consent (Appendix C). If individuals are interested in participation, they will be given a warm handoff to study staff. Study staff will meet with patients at CID to complete the enrollment consent form (Appendix D). Participants will also be asked to complete the participant questionnaire at the baseline, midpoint (2-4 months post baseline) and endpoint (at least 6 months post baseline). They will also be asked to complete the Locator Form (Appendix F). Participants will enter the cohort and contribute data to the study from their first CAB-RPV LA injection and be followed in the EHR for a period at least 6 months to determine engagement in care and adherence. Data on clinical endpoints (appointment adherence, viral load, CD4, drug use etc.) will be collected from the EHR.

Cohort 3 Recruitment and Enrollment: EHR data will be used to match patients for Cohort 3 1:1 to patients in Cohort 1 based on the following variables: history of drug use, housing status, sex. Patients in cohort 3 will be a prospective cohort of patients who are HIV positive and not receiving CAB-RPV LA. The Clinical Data Warehouse will match 10 participants to every 1 enrolled in Cohort 1 based on the variables above. CID staff will approach potential participants to assess interest in participation. If individuals are interested in participating, they will be given a warm handoff to the project manager to complete the Enrollment Consent form (Appendix D). They will also be asked to complete the Locator Form (Appendix G). The remainder of their study activity will mirror that of Cohort 2.

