7.7 Missed Injection Target Dose Timeline

Protocol Title: **CAB-RPV LA Implementation Strategies for High-Risk Populations**

In order to ensure that patients receive their injection within the 7 days of their target injection date, the following outline will be followed. This outline is applicable for any missed dose:

- **Day 1 Post Target:** The study team will outreach to the participant via their preferred communication method as specified in their locator form in order to encourage them to return within the following three days. The encounter will be tracked in the study Log Book.
- **Day 3 Post Target:** The study team will outreach again to the participant via the preferred communication method to encourage them to return the following day. The encounter will be tracked in the study Log Book.
- **Days 5-7 Post Target:** The study team will enlist BMC's ARCH and PT street-based outreach workers who are experienced with and successful at reaching and engaging high-risk patients. The outreach workers will conduct active outreach to the participant in the community to bring them in for a visit. If active outreach is unsuccessful, the study team will also use the contacts on the locator form to attempt to reach the participant. The encounter will be tracked in the study Log Book.
- **Upon Return Within 14 Days Post Target:** The study clinician will obtain a viral load and genotype. If the participant's viral load is less than 200 copies per mL, they will administer the CAB-RPV LA. If the participant's viral load is over 200 copies per mL, the study clinician will refer them to their primary care provider who will make the determination about whether or not an injection is appropriate. The encounter will be tracked in the study Log Book.
- **If participant returns after 15 days Post Target:**
 - **Missed Dose Occurs within 2 months of Initiation Injection:** The participant will be given a maintenance dose at their next contact with study staff (400mg/600mg 2 ml). The participant will then resume their normally scheduled injection plan, i.e. next injection scheduled to be given 25-32 days after maintenance dose administered.
 - **Missed Dose Occurs after first 2 months of injection:** The participant will be given a loading dose instead of their scheduled dosing amount (600mg/900 mg 3 ml). The participant will then resume their normally scheduled injection plan.

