11.2 Sample Size Calculation

For the pilot study, we have powered our study to address hypothesis 4 above. Our power calculation is as follows: With a total of 60 participants, 20 patients in each cohort, the study will have the statistical power to detect clinically meaningful differences in both engagement in care (appointment adherence) and undetectable viral load at 6 months. Depending on appointment adherence and undetectable viral load in the standard of care control group, we will be able to detect a minimum 40% difference, assuming 80% power and type 1 error probability (alpha) = 0.05. Estimates from our study sites suggest that undetectable viral load can be as low as 50% at any given time in our high-risk population. If we observe this level in the standard of care control group at 6 months, we will be able to observe a difference of 40% (or 90% vs. 50%) between the Cohort 1 CAB-RPV LA in the CBOc arm vs. the Cohort 2 CAB-RPV LA in the clinic arm and Cohort 1 CAB-RPV LA in the CBO arm vs. Cohort 3 no CAB-RPV LA arm participants, respectively. Because our intention to treat (ITT) analytic approach may mean an even lower proportion in controls (because missing data will be considered detectable), we believe our sample size is sufficient to yield rigorous clinical outcomes.

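### The powered 6-month viral load outcome has no scheduled test and no result window, and counting missing results as detectable would favour Cohort 1 if Cohort 3 has more of them

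*Combined protocol and SAP*

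**What the plan says.** Section 11.2 states that "we have powered our study to address hypothesis 4 above". Section 11.1 defines H4 as superior viral suppression at 6 months in the community-based arm compared with the matched controls of Cohort 3.

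The viral load comes from routine records. Section 6.0 takes surveys from participants and clinical data from the EHR, and adds that "no other data will be collected directly from study participants for Objective 2". Section 7.2 says of Cohort 2, whose procedures Cohort 3 mirrors: "Data on clinical endpoints (appointment adherence, viral load, CD4, drug use etc.) will be collected from the EHR". Sections 7.3 and 10.1 describe the same chart review. The evaluation table in Section 7.1 lists data collection for all cohorts, and injections and metabolic panels (months 1 and 4) for Cohort 1. It lists no viral load at midpoint or endpoint for anyone.

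The viral loads that the protocol does require are Cohort 1 screening and initial labs, and draws triggered by events. One trigger is a late return for an injection (Section 7.7): "The study clinician will obtain a viral load and genotype". The other is a suspected accidental IV dose (Section 7.10).

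In the primary intention-to-treat analysis (Section 11.3), "In cases of missing viral load data, we will treat the result as detectable". Section 11.2 remarks that this may lower the proportion in controls further, and offers that as support for the sample size.

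**The concern.** Counting a missing result as a failure is conservative for a single arm's suppression rate. It is not conservative for a difference between cohorts when the comparison cohort is tested less often, because each untested control then counts as unsuppressed.

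There is reason to expect unequal testing. Of the two cohorts compared in H4, only Cohort 1 has injection visits, street outreach after a missed dose, and a viral load on late return. Section 11.2 itself expects missing data to pull the control proportion down, and treats that as helpful to the comparison.

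A Cohort 3 participant who completes every survey but has no lab result in the chart is not a dropout, yet is scored as a failure. A positive H4 could therefore partly reflect who was tested, and no planned analysis would separate that from a real effect.

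**Working it through.** **1. The plan's own figure.** Section 11.2 gives "With a total of 60 participants, 20 patients in each cohort" and says "we will be able to detect a minimum 40% difference, assuming 80% power and type 1 error probability (alpha) = 0.05". The example is 90% against 50%. The two-sided formula with pooled variance and no continuity correction is

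n = [1.96·√(2·p̄·(1−p̄)) + 0.8416·√(p₁(1−p₁) + p₂(1−p₂))]² / (p₁−p₂)²

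With p₁ = 0.9, p₂ = 0.5 and p̄ = 0.7 this is [1.96·√0.42 + 0.8416·√0.34]² / 0.16 = (1.270 + 0.491)² / 0.16 ≈ 19.4, so 20 per cohort. Approximate power at 20 is 81.3%; exact power is 83.8% (chi-square) or 74.2% (Fisher). The stated sample size reproduces. The issue is how the outcome is ascertained.

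**2. Inputs for the check.**
- From the plan: 20 per cohort, alpha 0.05, missing counted as detectable.
- True suppression s, set equal in both cohorts so that any difference is false. The plan's only anchor for the standard-of-care group is that "undetectable viral load can be as low as 50% at any given time in our high-risk population"; its Cohort 1 example is 90%. I use 50%, 80% and 90%.
- Missing fractions m₁ and m₃ for Cohorts 1 and 3. The documents give none, so these are assumptions; the main case is 5% and 25%.

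**3. Formulas.** Observed proportion = s·(1−m). False difference = s·(m₃−m₁). The rejection probability is the exact sum of binomial probabilities over all 20-against-20 outcomes with two-sided p ≤ 0.05, unadjusted.

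**4. Main case, 5% against 25% missing.**

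| True suppression | Cohort 1 observed | Cohort 3 observed | False difference | Chi-square rejects | Fisher rejects |
|---|---|---|---|---|---|
| 50% | 0.475 | 0.375 | 10 points | 9% | 5% |
| 80% | 0.760 | 0.600 | 16 points | 20% | 12% |
| 90% | 0.855 | 0.675 | 18 points | 27% | 17% |

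Nearly all of these rejections favour Cohort 1.

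**5. Other assumptions.**
- Equal missingness (5% in each): false difference 0; chi-square rejects 4.3% at 50% suppression and 4.9% at 90%.
- 5% against 20%: chi-square rejects 6.9% at 50%, and 14% to 18% at 80% to 90%.
- 0% against 40%: false difference 20 points at 50% and 36 points at 90%; the chance of a significant chi-square result favouring Cohort 1 is 24.5% and 76.3%.
- Reversed, 25% in Cohort 1 against 5% in Cohort 3: a significant result favouring Cohort 1 has probability at most 0.4%, so the bias works against H4.

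**6. Whether the planned analyses test the rule.** Section 11.3 plans a check of completeness, a comparison of dropouts, and per-protocol logistic models. The first two are descriptive. The per-protocol set is not defined and is not described as relaxing the missing-data rule. Adjustment for baseline covariates does not undo an outcome scored as a failure because no test was done.

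**The case against.** The strongest reply is that the direction is inferred. The documents give no lab frequency for any cohort, and an injection visit is not a viral load. Draws on late return need not fall near month 6, and they select participants more likely to be detectable. Some Cohort 1 participants may come from outside the centre and have thinner records. All of this stands.

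A reader might infer that Cohort 3 has routine care only and will certainly have fewer results, so that H4 is biased towards Cohort 1. The documents do not support that. Cohort 3 patients are enrolled in care at the clinic, complete a locator form, receive reminders one week and one day before survey contacts, and are paid for surveys. The same chart extraction covers everyone. These features narrow any gap in testing, though none of them requires a viral load.

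A reader might also quote only the 20 to 27% rejection rates. Those need 80 to 90% true suppression in both cohorts and a chi-square test. At the plan's 50% figure the same missing rates give 9%, or 5% with Fisher. The planned H4 model is a multivariable logistic regression, so the unadjusted figures are only indicative.

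Finally, this is a non-randomised pilot, and the plan presents its missing-data rule as one used in other studies. That bears on priority. It does not supply a result window or a test of the rule.

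**Conclusion.** The point holds as a conditional one. The text establishes that the powered outcome has no scheduled follow-up test, no window for the 6-month result, a missing-equals-detectable rule, and no sensitivity analysis of that rule. It does not establish that Cohort 3 will have more missing results. That is plausible from the difference in contact and from the remark in Section 11.2, but it remains an assumption.

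If missingness differs by 20 points in that direction, the false difference is 10 to 18 points against the 40 the study is powered to detect. The error rate then runs from about nominal (Fisher, 50% suppression) to 27% (chi-square, 90% suppression). Equal missingness creates no false difference when true rates are equal. The change is cheap and should be made; the sample size needs no change on this account.

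**What to change.** In Sections 7.3 and 11.3:

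- Define one viral load window for all cohorts: the EHR result nearest 6 months within the 6 to 8 month endpoint window of Section 6.0. Sections 7.2 and 7.3 say only at least 6 months, so align them.
- Report the number of missing viral loads by cohort.
- Keep missing counted as detectable as the primary rule.
- Add a complete-case analysis.
- Add a tipping-point analysis that varies the assumed suppression rate among missing results separately in Cohorts 1 and 3. Giving missing Cohort 3 results that cohort's observed rate would not do, because it only reproduces the complete-case estimate. Complete-case alone is not enough either, since untested patients may be less often suppressed than tested ones.
- Describe H4 as supported only if the complete-case result agrees, and report the missing-data assumption at which the conclusion changes.

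The cost is SAP wording and a little more analysis on data already being collected, and H4 may look less favourable. These steps do not equalise testing between cohorts; they show how far the conclusion depends on it.

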5.0 Study Subject Selection

5.1 Subject Inclusion Criteria

Cohort 1: Age \geq 18 years, English or Spanish speaking, HIV-positive, labs indicate that they are a candidate for the medication and virally suppressed, meaning that their HIV-1 ribonucleic acid is less than 50 copies per mL. Individuals enrolled in Cohort 1 must be willing to complete the locator form (Appendix G) in order to receive appointment reminders prior to their monthly/bi-monthly injection and ongoing follow-up by outreach and study staff to maximize potential for adherence.

Cohort 2: Currently enrolled in care at CID and receiving CAB-RPV LA injection, age \geq 18 years, English or Spanish speaking. Individuals enrolled must be willing to complete the locator form in order to receive appointment reminders prior to follow-up data collection.

Cohort 3: Enrolled in care at CID but not receiving CAB-RPV LA, age \geq 18 years, matched to participants demographically and in terms of other characteristics in Cohort 1 at a 1:1 ratio. Individuals in Cohort 3 will be receiving the Standard Care for HIV treatment in CID. Standard of care for this group includes access to regular appointments with their HIV provider, oral ART, case management services, etc. Individuals enrolled must be willing to complete the locator form in order to receive appointment reminders prior to follow-up data collection.

Our goal for all three cohorts is to enroll a percentage of women that is equivalent to the number of female patients served by the sites, approximately 20-30% female. Similarly, we will ensure that our sample includes individuals of color proportional to their representation within the setting across all three cohorts.

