If the participant chose's to not take the oral lead-in mediation, the participant will proceed directly to the initiation injection once they have completed all required lab work, including HIV labs confirming that they are virally suppressed (> 50 copies per mL), and a comprehensive metabolic panel. The participant and their clinician will determine a date for the initiation injection. As the medication will need to be obtained from the pharmacy, participants will not be able to receive their initiation injection on the same day as they are enrolled into the study.

- At the time of the injection, during the 15 minute waiting period, study staff will sit with the participant and remind them of the target date for the next injection. This date will be recorded in the study Log Book. The month following the initiation dose, participants receive a maintenance dose. Once the participant has received the maintenance dose, the participant and their clinician may discuss whether the participant would like to shift to receiving the injection every other month rather than every month. The clinician and the participant may choose whether to receive the injection every month, or every other month per CID standard of care and the medication package insert.
- One week prior to each scheduled injection date, study staff will contact participant via their preferred contact method determined on the Locator Form to confirm injection date and confirm with the community-based clinician administering the injection.
- One day prior to injection date, study staff will contact participant for reminder.

Below is a table that outlines when all evaluation activities occur:

Month	Cohort 1	Cohort 2	Cohort 3
1	
• Screening• Enrollment• Comprehensive Metabolic Panel• Baseline Data Collection• Participant may choose to take 28 days of Oral Lead-In medication• If participant opts out of the oral lead-in, they will receive their Initiation Injection during this time point	
• Screening• Enrollment• Baseline Data Collection	
• Screening• Enrollment• Baseline Data Collection
2	
• Oral lead-in: Initial Injection• No Oral Lead-In: Maintenance Dose		

Protocol Title: **CAB-RPV LA Implementation Strategies for High-Risk Populations**

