11.0 Statistical Plan

11.1 Study Hypotheses

Objective 2 has the following hypotheses:

- **H1:** Changing the service site will result in $\geq 80\%$ of participants in the community-based intervention arm beginning injections
- **H2:** Of participants in the community-based intervention arm who begin injections, 80% will complete 6 injections
- **H3:** Changing the service site will result in improved engagement in care for participants in the community-based intervention arm compared to matched controls (Cohort 3) at 6 months for intervention patients compared to control group patients
- **H4:** Changing the service site will result in superior HIV viral suppression at 6 months compared to for participants in the community-based intervention arm compared to matched controls (Cohort 3)
- **H5:** Participants in the community-based intervention arm will be equally satisfied with their care compared to patients who receive care in clinic settings (Cohort 2).

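### Engagement in care (H3): events and trials are not defined, and if each person contributes several visits the planned model lacks a person-level variance

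*Combined protocol and SAP*

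**What the plan says.** H3 (Section 11.1) predicts "improved engagement in care for participants in the community-based intervention arm compared to matched controls (Cohort 3) at 6 months". The only gloss on the outcome is in Section 11.2: "engagement in care (appointment adherence". Sections 7.2 and 7.3 take appointment adherence from the EHR.

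Section 11.3 gives the model: "We will construct a multivariable logistic regression model with a logit link and the events/trials syntax to model the outcome". The equation holds an intercept, a cohort indicator, baseline factors and a symbol of which we are told only that it "is an error term". For viral load the same section plans a logistic regression "with a dichotomous outcome for undetectable viral load status at 6 months".

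The plan names no random effect, dispersion scale, generalised estimating equation or robust variance. It does not say which appointments are trials, what counts as kept, or how cancelled and rescheduled visits are handled.

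On timing, H3 is set at 6 months. Section 10.1 has EHR reviews at 3 and 6 months, Section 6.0 places the last follow-up at 6 to 8 months, and Section 7.2 follows the EHR for at least 6 months.

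**The concern.** Events/trials syntax is the form for y successes out of n attempts. If n is the number of visits scheduled for one person, those visits share that person's circumstances and are likely to be correlated. A binomial likelihood without a person-level term counts them as independent, so standard errors are too small and H3 could be declared significant because of the variance formula.

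The error term in the equation does not fill the gap. A binomial logit model has no additive residual, and the term is not defined at person level.

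The missing definition matters on either reading. If engagement is one yes/no per person, the attendance threshold that makes someone engaged is not stated. Either way, choices would be left until the data are in hand.

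**Working it through.** **1. The plan's own figure.** Section 11.2 gives 20 per cohort for 90% vs 50%, 80% power, alpha 0.05. Two-sided pooled formula:

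n = [1.96·√(2·0.7·0.3) + 0.842·√(0.5·0.5 + 0.9·0.1)]² / 0.4² = (1.270 + 0.491)² / 0.16 = 19.4, so 20 per arm (power 81.3%).

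This reproduces, and it assumes one yes/no result per person.

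**2. Inputs.**
- From the documents: 20 per cohort (11.2). From the regimen table in Section 7.0, Cohort 1 has 5-6 injections by month 6 if monthly and 3-4 if bi-monthly. Section 7.1 lets participants "shift to receiving the injection every other month rather than every month".
- Not in the documents: the Cohort 3 visit count (Section 5.1 says only "Standard of care for this group includes access to regular appointments with their HIV provider"), the attendance level, the within-person intraclass correlation (ICC), and whether injections count as trials.
- Assumed: 1-6 visits per person, 70% attendance, ICC 0.1 to 0.4.

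**3. Formula.** With m1 and m3 visits per person in Cohorts 1 and 3, and d = 1 + (m − 1)·ICC:

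SE factor = √[(d1/m1 + d3/m3) / (1/m1 + 1/m3)]

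True type I error ≈ 2·[1 − Φ(1.96 / SE factor)]

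Example, 4 vs 2 visits, ICC 0.3: d1 = 1.9, d3 = 1.3; (0.475 + 0.65)/(0.25 + 0.5) = 1.5; factor 1.22; type I error 11.0%.

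Example, 6 vs 6, ICC 0.3: factor √2.5 = 1.58; type I error 21.5%.

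**4. Simulation** (beta-binomial, 40,000 replicates per setting, 20 per arm, 70% attendance, unadjusted Wald test, pairs ignored). The last column is explained in step 5.

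| Visits, Cohort 1 vs 3 | SE factor, ICC 0.3 | Type I error, ICC 0.1 to 0.4 | Break-even pair correlation |
|---|---|---|---|
| 6 vs 6 | 1.58 | 11-26% | 0.83 |
| 6 vs 3 | 1.38 | 8-18% | 0.75 |
| 4 vs 3 | 1.31 | 8-16% | 0.71 |
| 6 vs 2 | 1.26 | 7-14% | 0.67 |
| 4 vs 2 | 1.22 | 6-13% | 0.62 |
| 3 vs 2 | 1.19 | 6-11% | 0.58 |
| 2 vs 2 | 1.14 | 6-10% | 0.50 |
| 4 vs 1 | 1.09 | 5-7% | 0.38 |
| 2 vs 1 | 1.05 | 5-6% | 0.25 |
| 1 vs 1 | 1.00 | no inflation | n/a |

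Attendance of 50% or 80% changes little (6 vs 6: 10.5-25.6%; 4 vs 2: 6.4-12.3%).

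**5. Matching.** Section 7.2 states: "EHR data will be used to match patients for Cohort 3 1:1 to patients in Cohort 1 based on the following variables" (drug use history, housing, sex). If attendance propensities within a pair correlate at r, the variance of the contrast falls by an amount proportional to 2·r·ICC. The naive standard error is then right when

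r = [(m1 − 1)/m1 + (m3 − 1)/m3] / 2.

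The ICC cancels. With 4-6 visits in Cohort 1 and 2-6 in Cohort 3 this is about 0.6-0.8; at 2 vs 2 it is 0.5. Simulated with pairs ignored (20,000 replicates), r = 0.3 gives 9-20% (6 vs 6), 7-15% (6 vs 3) and 6-9% (4 vs 2). At r = 0.7 the figures are 6-10%, 5-6% and about 4.5%.

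**6. The remedy.** A Pearson dispersion scale with a t reference on 38 df gives 4-5% at 6 vs 6 and 2-4% at 6 vs 2.

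**The case against.** The case for reading engagement as one result per person is real. Section 11.2 sizes engagement and viral load together as a comparison of 20 people with 20 people. Section 11.3 introduces the viral load model as being similar to the engagement model, which weakens the contrast with an explicitly dichotomous outcome. This stands, so the variance point is conditional. A reader might infer that the H3 test is certainly anticonservative; the documents do not settle that.

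Nor do they show that injection visits are the trials. Section 7.11 says many participants keep seeing their usual provider. If only provider appointments common to both cohorts count, there may be few per person, and the inflation is small. The 26% needs Cohort 3 to have as many visits as people injected monthly, together with a high ICC.

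It may also be tempting to say that any positive within-person correlation inflates the error. The matching prevents that general claim: a strong within-pair correlation can offset it. No document gives the pair correlation, however, and no paired analysis is planned.

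A reader might say that no window is given at all. That goes too far: 6 months is stated for H3, with EHR reviews at 3 and 6 months. What is unsettled is the exact start and stop of counting.

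Finally, this is a pilot and H3 is not the hypothesis used for sizing. That limits the consequence, but H3 is a listed comparative hypothesis, and Section 11.2 claims power for engagement at alpha 0.05.

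**Conclusion.** The concern holds in conditional form. It is certain that events, trials and the exact counting period are undefined. If a person contributes more than one visit, which the syntax and the EHR appointment data suggest, the planned model has no allowance for within-person correlation. Standard errors for H3 are then too small unless Cohort 3 has about one visit each or the within-pair correlation is strong.

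With two or more Cohort 3 visits, the type I error runs from about 6% to 26% before any matching effect. All sizes rest on assumed visit counts, attendance and ICC. H4 has one binary result per person and is not affected; the sample size is not in question. The plan should be changed before analysis, with medium confidence about the reading.

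**What to change.** 1. Define engagement: which visits are trials, what counts as kept, how cancelled and rescheduled visits count, and one start and stop of counting for all cohorts. Reconcile the timings in Sections 6.0, 7.2, 10.1 and 11.1.
2. If the outcome is one yes/no per person, state the attendance threshold; the variance needs no change.
3. If there is more than one trial per person, keep the events/trials logit model and add a person-level variance. Use either a Pearson dispersion scale with a t reference on participant-level degrees of freedom, or a small-sample robust standard error clustered on the person. For Cohort 1 vs Cohort 3, clustering on the matched pair is an alternative if the pair is recorded; it covers both sources of correlation.

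The cost is a short definition and one model option, with no extra participants. Standard errors become about 1.1 to 1.6 times larger at ICC 0.3, which is the uncertainty the naive model hides. The Pearson scale is somewhat conservative (about 2-4%) when visit counts differ between cohorts. Pair clustering uses 19 rather than 38 degrees of freedom, a critical value about 3% larger.
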